9.5 Protocol Amendment 2, 28Mar2018

Text revisions resulting from this amendment are incorporated into the body of Protocol Amendment 2. Estimated GFR criteria were removed and changed to CrCl throughout. Copyediting and formatting errors were corrected throughout; notably, the term “glutamine” dehydrogenase was corrected to “glutamate” dehydrogenase throughout the document. Breastfeeding exclusion criterion was added. Additionally, table numbering was changed to sequential numbering to align with new in-house authoring style. Major changes to the protocol are summarized below.

- 1 Section 1.7.2 (Secondary Hypotheses): The word “prevent” was replaced with “reduce” to align with the Protocol Synopsis.
- 2 Section 3.1.1 (Overview – Inpatient Phase – Cohorts A and B): Text was revised for Cohort B to remove $eGFR \geq 60$ and replace with subjects with $CrCl \geq 60 \text{ mL/min}$ (*Cockcroft Gault equation*) within 6 hours will undergo an index coronary CTA no earlier than 48 hours following the first dose. Changes were made to eGFR to correctly change to CrCl throughout as the Cockcroft Gault equation applies to CrCl.
- 3 Section 4.1.3 (Exclusion Criteria): Criterion 8 was revised to remove known $eGFR < 30 \text{ mL/min}/1.73 \text{ m}^2$ and replace with known $CrCl < 30 \text{ mL/min}$ (*Cockcroft Gault equation*) as a contraindication to MR imaging. Criterion 9 was revised to exclude women who are breastfeeding. Criterion 10 was added to exclude subjects who are currently or had previously participated in a study using an investigational therapy or devices within the last 30 days.
- 4 Section 4.1.4 (Additional Study Procedure Requirements – Cardiovascular MRI and Coronary CTA): Text in Cardiovascular MRI subsection was revised to remove $eGFR \geq 30 \text{ mL/min}/1.73 \text{ m}^2$ and replace with CrCl to read that MRI would be allowed if there were no contraindications to MR imagining (eg, metallic implant, claustrophobia, ICD, pacemaker), but for subjects to receive contrast they must meet the requirements of $CrCl \geq 30 \text{ mL/min}$ (*Cockcroft Gault equation*) within 7 days prior to the procedure, and no known allergy to gadolinium contrast agents. This was revised for clarification and to provide a breakdown of MRI criteria to allow MRI (without using contrast) in subjects with no MRI contraindications who cannot receive contrast. The Coronary CTA subsection was revised to remove $eGFR \geq 60 \text{ mL/min}/1.73 \text{ m}^2$ and replace with $CrCl \geq 60 \text{ mL/min}$ (*Cockcroft Gault equation*) within no more than 6 hours prior to index CTA and no more than 7 days prior to follow up.
- 5 Section 4.1.5 (Subject Enrollment and Randomization): Text was revised to clarify that randomization will be stratified by infarct location, ensuring balanced randomization to active treatment vs placebo within the anterior and the non-interior MI groups.
- 6 Table 8 (Treatment Period and Follow-up Period Procedures: Cohort A [REDACTED]) and Table 9 (Treatment Period and Follow-up Period Procedures: Cohort B [REDACTED])

[REDACTED] A PK blood sample was added to Table 8 (Cohort A) for Day 31 to align with Cohort B. Record vital signs at Screening was added to Table 9 (Cohort B) to align with Cohort A.

7 Section 4.3.1 (Medical History and Physical Examination, Weight, and Vital Signs): Text was revised to correct that full physical examination will be conducted anytime between Day 1 and 3 prior to administration of Dose [REDACTED]. Additionally, “on all days” was deleted from text for measurement of vital signs to align with Schedule of Study Procedures.

8 Section 4.3.8 (Imaging Biomarker Evaluation and Methods) – [REDACTED]

[REDACTED]

9 Section 4.5.1.4 (Treatment Administration): Text was revised to add that subjects should be instructed on whether their regular medication can be taken while fasting. This was added for clarification and as a reminder to the investigator to review specific concomitant medication instructions with subjects.

10 Section 4.5.1.5 (Monitoring of Dose Administration): Text was revised to remove “before and after dose administration” to align with Schedule of Study Procedures.

11 Section 4.8.8 (Interim Analysis) and Synopsis: Text was added to clarify that the sponsor and Principal Investigator will monitor the statistical assumptions in a blinded fashion and decide the exact time for interim analyses.

9.6 Protocol Amendment 1, 09Jan2018

Text revisions resulting from this amendment are incorporated in the body of Protocol Amendment 1. Copyediting and formatting errors were corrected throughout. Major changes to the protocol are summarized below.

1 Section 4.2.1 (Enrollment and Treatment Period), **Table 8** (Treatment Period and Follow-up Procedures: Cohort A [REDACTED]): Footnotes a and b were added due to previous omission; footnote h was replaced by footnote g for PK blood sample on Day 1 due to previous error; footnote i was replaced by footnote h for PD blood sample on Day 1, 1-1.5 hour post-dose due to previous error.

2 Section 4.5.1.1 (Investigational Product Handling): [REDACTED]

3 Section 4.3.8 (Imaging Biomarker Evaluation and Methods), [REDACTED]

[REDACTED]

10.2 Appendix 2 – Contraception Guidance

For females:

Females without childbearing potential will be included in this study. Females without childbearing potential are defined as those who are surgically sterile (ie, surgical sterilization includes bilateral tubal ligation, bilateral oophorectomy, or hysterectomy) or those who are postmenopausal (defined as 12 months with no menses without an alternative medical cause).

For males:

Nonsterilized males who are sexually active with a female partner of childbearing potential must use condom and spermicide from Day 1 through the end of their participation in the study. Because male condom and spermicide is not a highly effective contraception method it is strongly recommended that female partners of a male study subjects also use a highly effective method of contraception throughout this period. A highly effective method of contraception is defined as one that results in a low failure rate (ie, less than 1% per year) when used consistently and correctly. The acceptable methods of contraception are described in [Table 13](#).

Table 13 Highly Effective Methods of Contraception

Barrier Methods	Hormonal Methods

 • Intrauterine device • Intrauterine hormone-releasing system (UIS)^a • Bilateral tubal occlusion • Vasectomized partner^b • Sexual abstinence^c 	
Combined (estrogen and progestogen containing hormonal contraception)
 
 ◦ Oral (combined pill) ◦ Injectable ◦ Transdermal (patch) 
Progestogen-only hormonal contraception associated with inhibition of ovulation^d
 
 ◦ Injectable ◦ Implantable ◦ Intravaginal

^a This is also considered a hormonal method.

^b With appropriate post-vasectomy documentation of surgical success (absence of sperm in ejaculate).

^c Sexual abstinence is considered a highly effective method only if defined as refraining from heterosexual intercourse during the entire period of the study and if it is the preferred and usual lifestyle of the subject.

^d Progestogen-only hormonal contraception, where inhibition of ovulation is not the primary mode of action (eg, minipill), is not accepted as a highly effective method.

10.3 Appendix 3 - Additional Safety Guidance

Further Guidance on the Definition of a Serious Adverse Event (SAE)

Life threatening

‘Life-threatening’ means that the subject was at immediate risk of death from AE as it occurred or it is suspected that use or continued use of the product would result in the subject’s death. ‘Life-threatening’ does not mean that had an AE occurred in a more severe form it might have caused death (eg, hepatitis that resolved without hepatic failure).

Hospitalization

Outpatient treatment in an emergency room is not in itself a serious AE, although the reasons for it may be (eg, bronchospasm, laryngeal edema). Hospital admissions and/or surgical operations planned before or during a study are not considered AEs if the illness or disease existed before the subject was enrolled in the study, provided that it did not deteriorate in an unexpected way during the study.

Important Medical Event or Medical Intervention

Medical and scientific judgment should be exercised in deciding whether a case is serious in situations where important medical events may not be immediately life threatening or result in death, hospitalization, disability or incapacity but may jeopardize the subject or may require medical intervention to prevent one or more outcomes listed in the definition of serious. These should usually be considered as serious.

Simply stopping the suspect drug does not mean that it is an important medical event; medical judgment must be used.

Examples of such events are:

- Angioedema not severe enough to require intubation but requiring intravenous hydrocortisone treatment
- Hepatotoxicity caused by paracetamol (acetaminophen) overdose requiring treatment with N-acetylcysteine
- Intensive treatment in an emergency room or at home for allergic bronchospasm
- Blood dyscrasias (eg, neutropenia or anemia requiring blood transfusion) or convulsions that do not result in hospitalization
- Development of drug dependency or drug abuse

Assessment of Severity

Assessment of severity is one of the responsibilities of the investigator in the evaluation of AEs and SAEs. The determination of severity should be made by the investigator based upon medical judgment and the severity categories of Grade 1 to 5 as defined below.

Grade 1	An event of mild intensity that is usually transient and may require only minimal treatment or therapeutic intervention. The event does not generally interfere with usual activities of daily living.
Grade 2	An event of moderate intensity that is usually alleviated with additional specific therapeutic intervention. The event interferes with usual activities of daily living, causing discomfort but poses no significant or permanent risk of harm to the subject.
Grade 3	A severe event that requires intensive therapeutic intervention. The event interrupts usual activities of daily living, or significantly affects the clinical status of the subject.
Grade 4	An event, and/or its immediate sequelae, that is associated with an imminent risk of death
Grade 5	Death as a result of an event.

It is important to distinguish between serious criteria and severity of an AE. Severity is a measure of intensity whereas seriousness is defined by the criteria in Section 5.3. A Grade 3 AE need not necessarily be considered an SAE. For example, a Grade 3 headache that persists for several hours may not meet the regulatory definition of an SAE and would be considered a nonserious event, whereas a Grade 2 seizure resulting in a hospital admission would be considered an SAE.

Assessment of Relationship

Relationship to Investigational Product

The investigator is required to provide an assessment of relationship of AEs and SAEs to the investigational product. The following factors should be considered when deciding if there is a “reasonable possibility” that an AE may have been caused by the investigational product.

- Time Course. Exposure to suspect investigational product. Has the subject actually received the suspect investigational product? Did the AE occur in a reasonable temporal relationship to the administration of the suspect investigational product?
- Consistency with known investigational product profile. Was the AE consistent with the previous knowledge of the suspect investigational product (pharmacology and toxicology) or products of the same pharmacological class? OR could the AE be anticipated from its pharmacological properties?
- De-challenge experience. Did the AE resolve or improve on stopping or reducing the dose of the suspect investigational product?

- No alternative cause. The AE cannot be reasonably explained by another etiology such as the underlying disease, other drugs, or other host or environmental factors.
- Re-challenge experience. Did the AE reoccur if the suspected investigational product was reintroduced after having been stopped? MedImmune would not normally recommend or support a re-challenge.
- Laboratory tests. A specific laboratory investigation (if performed) has confirmed the relationship?

In difficult cases, other factors could be considered such as:

- Is this a recognized feature of overdose of the investigational product?
- Is there a known mechanism?

Causality of ‘related’ is made if following a review of the relevant data, there is evidence for a ‘reasonable possibility’ of a causal relationship for the individual case. The expression ‘reasonable possibility’ of a causal relationship is meant to convey, in general, that there are facts (evidence) or arguments to suggest a causal relationship.

The causality assessment is performed based on the available data including enough information to make an informed judgment. With limited or insufficient information in the case, it is likely that the event(s) will be assessed as ‘not related’.

Causal relationship in cases where the disease under study has deteriorated due to lack of effect should be classified as no reasonable possibility.

Relationship to Protocol Procedures

The investigator is also required to provide an assessment of relationship of SAEs to protocol procedures on the SAE Report Form. This includes nontreatment-emergent SAEs (ie, SAEs that occur prior to the administration of investigational product) as well as treatment-emergent SAEs. A protocol-related SAE may occur as a result of a procedure or intervention required during the study (eg, blood collection, washout of an existing medication). The following guidelines should be used by investigators to assess the relationship of SAEs to the protocol:

Protocol related: The event occurred due to a procedure/intervention that was described in the protocol for which there is no alternative etiology present in the subject’s medical record.

Not protocol related: The event is related to an etiology other than the procedure/intervention that was described in the protocol (the alternative etiology must be documented in the study subject’s medical record).

10.4 Appendix 4 - National Institute of Allergy and Infectious Disease and Food Allergy and Anaphylaxis Network Guidance for Anaphylaxis Diagnosis

National Institute of Allergy and Infectious Disease (NAID) and Food Allergy and Anaphylaxis Network (FAAN) define anaphylaxis as a serious allergic reaction that is rapid in onset and may cause death. They recognize 3 categories of anaphylaxis, with criteria designated to capture from 80% of cases (category 1) to > 95% of all cases of anaphylaxis (for all 3 categories).

- 1 Acute onset of an illness (minutes to several hours) with involvement of the skin, mucosal tissue, or both (eg, generalized hives, pruritus or flushing, swollen lips-tongue-uvula)
AND AT LEAST ONE OF THE FOLLOWING:
 - (a) Respiratory compromise (eg, dyspnea, wheeze-bronchospasm, stridor, reduced peak expiratory flow (PEF), hypoxemia)
 - (b) Reduced blood pressure (BP) or associated symptoms of end-organ dysfunction (eg, hypotonia [collapse], syncope, incontinence)
- 2 Two or more of the following that occur rapidly after exposure to a likely allergen for that patient (minutes to several hours):
 - (a) Involvement of the skin-mucosal tissue (eg, generalized hives, itch-flush, swollen lips-tongue-uvula)
 - (b) Respiratory compromise (eg, dyspnea, wheeze-bronchospasm, stridor, reduced PEF, hypoxemia)
 - (c) Reduced BP or associated symptoms (eg, hypotonia [collapse], syncope, incontinence)
 - (d) Persistent gastrointestinal symptoms (eg, crampy abdominal pain, vomiting)
- 3 Reduced BP after exposure to known allergen for that patient (minutes to several hours):
 - (a) Infants and children: low systolic BP (age specific) or greater than 30% decrease in systolic BP
 - (b) Adults: systolic BP of less than 90 mm Hg or greater than 30% decrease from that person's baseline

10.5 Appendix 5 - Actions Required in Cases of Increases in Liver Biochemistry and Evaluation of potential serious liver injury corresponding to Hy's Law

10.5.1 Introduction

This appendix describes the process to be followed to identify and appropriately report cases of potential serious liver injury corresponding to Hy's Law. It is not intended to be a comprehensive guide to the management of elevated liver biochemistries.

During the course of the study, the investigator will remain vigilant for increases in liver biochemistry. The investigator is responsible for determining whether a subject meets criteria for potential serious liver injury corresponding to Hy's Law at any point during the study.

The investigator participates, together with MedImmune clinical project representatives, in review and assessment of cases meeting criteria for potential serious liver injury corresponding to Hy's Law to agree whether these criteria are met. This is the case if there is no alternative explanation for the elevations in liver biochemistry other than drug-induced liver injury (DILI) caused by the investigational product.

The investigator is responsible for recording data pertaining to cases of potential serious liver injury corresponding to Hy's Law, and for reporting AEs and SAEs according to the outcome of the review and assessment in line with standard safety reporting processes.

10.5.2 Definitions

10.5.2.1 Potential serious liver injury corresponding to Hy's Law

- ALT and total bilirubin (TBL) normal at baseline:
ALT $> 3 \times$ upper limit of normal (ULN), with associated elevation in glutamate dehydrogenase (GLDH), without corresponding CK and/or troponin elevation, **together with** TBL $\geq 2 \times$ ULN, at any point during the study following the start of study medication, irrespective of an increase in alkaline phosphatase (ALP).
- ALT or TBIL abnormal at baseline:
ALT $> 3 \times$ baseline or > 300 U/L (whichever occurs first), with associated elevation in GLDH, without corresponding CK and/or troponin elevation, **together with** TBL $\geq 2 \times$ ULN, or, if abnormal at baseline, $> 2 \times$ bsl, at any point during the study following the start of study medication, irrespective of an increase in alkaline phosphatase (ALP).

If ALT is decreasing from baseline, nadir will be new baseline

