10.5.3 Identification of cases of (potential) serious liver injury corresponding to Hy's law

In order to identify cases of (potential) serious liver injury corresponding to Hy's law, it is important to perform a comprehensive review of laboratory data for any subject who meets any of the following identification criteria in isolation or in combination:

ALT and TBIL normal at baseline:

- ALT $> 3 \times$ ULN, with associated elevation in GLDH
- TBL $\geq 2 \times$ ULN

ALT or TBIL abnormal at baseline:

- ALT $> 3 \times$ ULN, with associated elevation in GLDH, or, if abnormal at baseline, ALT $> 3 \times$ baseline or > 300 U/L (whichever occurs first), with associated elevation in GLDH,
- TBL $\geq 2 \times$ ULN, or, if abnormal at baseline, $> 2 \times$ bsl

If ALT is decreasing from baseline, nadir will be new baseline

When a subject meets any of the identification criteria, in isolation or in combination, the central laboratory will immediately send an alert to the investigator (also sent to sponsor study representative).

The investigator will also remain vigilant for any local laboratory reports where the identification criteria are met, where this is the case the investigator will:

- Notify the sponsor study representative
- Request a repeat of the test (new blood draw) by the central laboratory
- Complete the appropriate unscheduled laboratory case report form (CRF) module(s) with the original local laboratory test result

When the identification criteria are met from central or local laboratory results the investigator will without delay:

- Determine whether the subject meets criteria for (potential) serious liver injury corresponding to Hy's law (see Section 10.5.4.2) by reviewing laboratory reports from all previous visits (including both central and local laboratory results)

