10.6 Appendix 6 - Management of Liver Toxicity

In the setting of acute MI, transaminases used to monitor for liver toxicity (ALT and AST) can be elevated and of cardiac origin. [Table 14](#) describes actions to be taken according to ALT; GLDH; total bilirubin; and subject symptoms.

Table 14 Actions to be Taken According to ALT, Glutamate Dehydrogenase, Total Bilirubin

Treatment-emergent ALT		Treatment-emergent TBL	Liver Symptoms	Action
1	If normal at baseline: ALT > 3 x ULN, with associated elevation in GLDH, without corresponding CK and troponin elevation	Normal	None	Repeat ALT, AST, ALP, TBL, in 24-48 hours Follow-up for symptoms.
	If abnormal at baseline: ALT > 2 x baseline or > 200 U/L (whichever occurs first), with associated elevation in GLDH, without corresponding CK and troponin elevation If ALT is decreasing from baseline, nadir will be new baseline.	For patients with abnormal bsl, No change in baseline TBL		

Table 14 Actions to be Taken According to ALT, Glutamate Dehydrogenase, Total Bilirubin

Treatment-emergent ALT		Treatment-emergent TBL	Liver Symptoms	Action
2	If normal at baseline: ALT > 5 x ULN, with associated elevation in GLDH, without corresponding CK and troponin elevation	Normal	None	Interrupt study drug. Initiate close monitoring and workup for competing etiologies.
	If abnormal at baseline: ALT > 3 x baseline or > 300 U/L (whichever occurs first), with associated elevation in GLDH, without corresponding CK and troponin elevation If ALT is decreasing from baseline, nadir will be new baseline	For patients with abnormal bsl, No change in baseline TBL		Study drug can be restarted only if another etiology is identified and liver enzymes return to baseline.
3	If normal at baseline: ALT > 3 x ULN, with associated elevation in GLDH, without corresponding CK and troponin elevation	TBL > 2 x ULN	None	Interrupt study drug. Initiate close monitoring and workup for competing etiologies.
	If abnormal at baseline: ALT > 2 x baseline or > 200 U/L (whichever occurs first), with associated elevation in GLDH, without corresponding CK and troponin elevation If ALT is decreasing from baseline, nadir will be new baseline.	For patients with abnormal bsl, > 2 x bsl		Study drug can be restarted only if another etiology is identified and liver enzymes return to baseline.

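### For a subject with normal ALT but abnormal bilirubin at baseline, the Hy's law definition sets the ALT limit at 3 x baseline or 300 U/L, while the 10.5.3 ALT trigger and Table 14 set it at 3 x ULN or higher

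*Protocol*

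**What the plan says.** Protocol 10.5.2.1 (potential serious liver injury) and 10.5.2.2 (serious liver injury) split subjects by their baseline liver tests. The second stratum is headed "ALT or TBIL abnormal at baseline", so abnormal bilirubin alone is enough to enter it. Its only ALT limit is more than 3 times "baseline or > 300 U/L (whichever occurs first), with associated elevation in GLDH, without corresponding CK and/or troponin elevation". In the same bullet, the bilirubin limit has a separate clause for an abnormal baseline value. The ALT limit has no matching clause for a normal one.

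Section 10.5.3 repeats the stratum heading but words the ALT criterion differently: more than 3 times "ULN, with associated elevation in GLDH, or, if abnormal at baseline, ALT" above 3 x baseline or 300 U/L. Laboratory review is prompted when a subject "meets any of the following identification criteria in isolation or in combination".

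Table 14 (Appendix 6) splits its ALT column by baseline. Rows 1, 3 and 4 read "If normal at baseline: ALT > 3 x ULN, with associated elevation in GLDH, without corresponding CK and troponin elevation", and row 2 uses 5 x ULN. Bilirubin has its own column with its own baseline clause, which in row 3 is "For patients with abnormal bsl, > 2 x bsl". Rows 2, 3 and 4 are the ones that call for study drug to be interrupted.

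**The concern.** The subject in question has normal ALT and abnormal bilirubin at baseline. The definition measures a later ALT against that subject's own normal value. The ALT trigger and the action table measure it against ULN. A normal baseline cannot exceed ULN, so the definition's limit is the lower one, or at most equal.

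Two things are at stake. A subject can be a potential Hy's law case under Appendix 5 and still match no row of the protocol's own liver-action table, including the interruption rows. Also, 10.5.2.2 lets the ALT rise come before the bilirubin rise, with no time limit between them. If ALT rises first and stays inside the gap, the 10.5.3 ALT criterion gives no early alert.

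**Working it through.** **Inputs.** The limits come from Protocol 10.5.2.1, 10.5.2.2, 10.5.3 and Table 14. The documents give no ULN for ALT, so 35, 40 and 55 U/L are assumed, with baseline ALT of 10, 20 and 30 U/L and at ULN. The plan has no figure of its own to reproduce.

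**ALT limit for baseline ALT b (normal, so b ≤ ULN) with abnormal baseline bilirubin**

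| Place | ALT limit |
|---|---|
| 10.5.2.1 and 10.5.2.2 | above 3 x b, or above 300 U/L |
| 10.5.3, ALT criterion | above 3 x ULN |
| Table 14, rows 1, 3 and 4 | above 3 x ULN |
| Table 14, row 2 | above 5 x ULN |

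**Band of disagreement.** The definition's ALT limb is met and the others are not when 3 x b < ALT ≤ 3 x ULN. In whole U/L:

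| Assumed ULN | b = 10 | b = 20 | b = 30 | b = ULN |
|---|---|---|---|---|
| 35 | 31-105 | 61-105 | 91-105 | none |
| 40 | 31-120 | 61-120 | 91-120 | none |
| 55 | 31-165 | 61-165 | 91-165 | none |

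The disagreement runs one way: an ALT above 3 x ULN is always above 3 x b as well. The 300 U/L alternative never governs here, since 3 x ULN is at most 3 x 55 = 165.

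**Worked case (assumed values).** ULN is 40 and baseline ALT is 20. Bilirubin is 1.3 x ULN at baseline. Later ALT is 80 and bilirubin 2.8 x ULN, with GLDH raised and no CK or troponin rise.

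- Definition, ALT: 3 x 20 = 60 and 80 > 60, so met.
- Definition, bilirubin: 2 x 1.3 = 2.6 and 2.8 > 2.6, so met. The whole definition is met.
- 10.5.3, ALT criterion: 3 x 40 = 120 and 80 < 120, so not met.
- 10.5.3, bilirubin criterion: 2.8 > 2.6, so met. Review is prompted by bilirubin alone.
- Table 14, rows 1, 3 and 4: 80 < 120. Row 2: 5 x 40 = 200 and 80 < 200. No row applies, although the row 3 bilirubin condition is satisfied.

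**Normal-range ALT.** If b < ULN/3, then 3 x b < ULN. With b = 10 and ULN = 40, an ALT of 31-40 is within the normal range and still passes the definition's ALT limb. It does not by itself meet the definition, which also needs the GLDH, CK/troponin and bilirubin conditions.

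**Nadir rule.** Section 10.5.2.1 adds "If ALT is decreasing from baseline, nadir will be new baseline". A falling ALT lowers b and widens the band.

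**The case against.** The strongest reply is that the appendix still works as a sequence, and most of it stands.

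- A reader might infer that 10.5.3 and 10.5.2 classify one case in opposite ways. They do not. Section 10.5.3 only prompts a review, and classification rests on 10.5.2. Anyone who meets the full definition has met its bilirubin limb, which is also a stand-alone criterion in 10.5.3. The investigator then reviews laboratory reports from all earlier visits, so an earlier ALT rise is recovered. What is lost is the early ALT alert.
- A reader might infer that the protocol lists no action for such a case. Section 10.5.4.2 lists sponsor notification, monitoring, work-up and SAE reporting, and 10.5.5 adds a joint review within 12 days. Section 4.1.7 separately allows dosing to stop for safety reasons. Only a Table 14 action is missing.
- A reader might infer that counts of treatment-emergent SAEs depend on which section is read. SAE reporting is tied to the Hy's law criteria in 10.5.2 and to the review outcome. Neither 10.5.3 nor Table 14 contains an SAE rule.
- Table 14 serves a different purpose, and its limits differ from 10.5.2 elsewhere too: for abnormal baseline ALT, rows 1, 3 and 4 use 2 x baseline or 200 U/L. Different limits alone are therefore no contradiction. In that stratum, however, those rows have lower ALT limits than the definition. Here the table's limit is higher, which opens the gap.

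The clause on an abnormal baseline could also be read as covering bilirubin. In 10.5.3 that would make the 3 x ULN limb redundant, because everyone in the stratum has an abnormal value. In Table 14 the clause sits in the ALT column, and bilirubin has its own. The ALT-specific reading is the natural one.

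**Conclusion.** The inconsistency is in the current text and does not depend on redacted material or the amendment log. For normal ALT with abnormal bilirubin at baseline, an ALT above 3 x baseline and up to 3 x ULN can complete the potential Hy's law definition while matching no Table 14 row. An ALT-first rise in that band gives no ALT-based alert.

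At a baseline of 20 U/L the band is 61-105, 61-120 or 61-165 U/L for an assumed ULN of 35, 40 or 55. It vanishes only when baseline ALT equals ULN. The widths rest on those assumed values, but the existence of the gap does not.

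The reach is small. Section 5.6.2 expects aminotransferases to be raised at inclusion in most of these patients, so normal ALT with abnormal bilirubin should be uncommon, and every accompanying condition must also hold. The documents do not support reading this as missed cases, a lack of follow-up or unstable SAE counts. It is still more than clerical, because a safety threshold differs between sections meant to work together. No view is taken on which limit is right.

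**What to change.** Reconcile 10.5.2.1, 10.5.2.2, 10.5.3 and Table 14 so that the ALT limit for a subject with normal ALT and abnormal bilirubin at baseline is consistent across all four, and so that every case meeting the 10.5.2 definition maps to a Table 14 row. The sponsor's safety physician decides which limit applies and what the row says. Then check the central-laboratory alert against the reconciled text; the documents do not show how it was programmed.

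The cost is protocol wording in four places and one alert check. No analysis changes.
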